Smoking cessation and the prevention of obesity are two of the most significant cancer prevention outcomes. Smokers who want to quit smoking and minimize weight gain have few, if any treatment options, despite two decades of post-cessation weight gain (PCWG) research. Identifying effective PCWG prevention approaches has the potential to remove a major barrier to the initiation and maintenance of smoking cessation, and to reduce the overweight and obesity problem in the US. To advance the science and practice of interventions to reduce PCWG, we propose to evaluate a novel application of a behavioral activation (BA) intervention to prevent PCWG in men and women. To date, PCWG prevention research has focused on women, even though 25% of the increase in the proportion of overweight men has been attributed to quitting smoking. If the hypotheses are supported, the findings would suggest that targeting reward-related mechanisms common to both smoking and eating: (1) is an effective approach to promoting smoking cessation, while minimizing PCWG; (2) is a viable approach for addressing two rewarding behaviors concurrently, without risking compensatory responses; and (3) can be used as an adjunct to pharmacotherapy. Finally, the findings have implications for improved treatments for multiple co-morbid health risk behaviors (obesity, alcohol, substance use), supporting a wide-ranging impact on the prevention of cancer and other diseases.

Behavioral theories, such as Behavioral Economic and Incentive Salience Theories suggest that PCWG may stem, in part, from the reward deficit produced by smoking cessation. Upon quitting, smokers lose a significant reinforcer, increasing the motivational salience of available alternative reinforcers. However, smokers typically have fewer alternative reinforcers from which to choose and may experience less pleasure from these reinforcers after quitting smoking. Compensatory increases in between-meal snacking on foods high in fat and sugar may offset the reward deficit due to quitting smoking. Highly palatable snack food is a readily available reinforcer that shares common reward mechanisms with nicotine. Behavioral Economic Theory indicates that the reinforcing value of snacking can be enhanced, or reduced, based on the availability of alternative reinforcers. Fewer alternative reinforcers and a reduction in pleasure derived from available reinforcers forge an over-reliance on palatable snack foods to substitute for the reinforcement previously derived from cigarettes. After quitting smoking, individuals may become more responsive to snack food cues, find snack foods more pleasant to eat and more reinforcing. Indeed, our research group has shown that smoking cessation increases the reinforcing value of snack foods, which predicts subsequent food intake and weight gain. To avoid smoking cessation-induced increases in food intake and weight gain that precipitate smoking relapse, it is key to evaluate novel behavioral interventions that target involvement in, and subjective reward derived from, alternative reinforcers.

To advance the science and practice of interventions to reduce PCWG, we propose to target reward-related mechanisms common to smoking and palatable food intake. Through a novel application of a behavioral activation intervention to smoking cessation and to PCWG (BAS+), we will increase opportunities for reinforcement and enhance the pleasure obtained from typical reinforcers. We propose a randomized clinical trial of BAS+ plus transdermal nicotine (TN) vs. Standard Smoking Cessation Counseling (SC) plus TN in treatment seeking smokers (ages 18-65). Participants will receive 8 individual BAS+ or SC sessions plus TN over a 10-week period.

CONFIDENTIAL

This material is the property of the University of Pennsylvania. Do not disclose or use except as authorized in writing by the study sponsor

The primary outcomes will be PCWG and 7-day point prevalence abstinence at 26 weeks after the target quit date. Food intake (secondary outcome) will be measured via 24-hour food recalls conducted over 3 consecutive days at pre-treatment, mid-treatment, end of treatment, and follow-up. Mediating mechanisms (e.g., alternative reinforcers, relative reinforcing value of food, food reward, and food cue-induced craving) will be assessed before, during, and at the end of treatment (week 8). Potential moderators include gender, depression symptoms and weight concerns.

1.2 *Background - Neuroimaging Sub-Study*

The parent randomized clinical trial of behavioral activation intervention (BAS+) integrates Behavioral Economic Theory and cognitive neuroscience research. The basic premise is that smoking cessation produces a reward dysregulation that increases the reward value of other reinforcers, such as highly palatable foods. Because food is a readily available reinforcer --and palatable foods increase in their incentive salience after quitting-- food cue-elicited reactivity in the brain's reward system would increase with smoking cessation. Food reward and reinforcing value also increases in the context of cessation leading to increased food intake. Cessation-induced increases in food reward are paralleled by decreases in the ability to control the consumption of palatable food. Research by our group and others shows that cessation impairs aspects of executive function that are critical to self-control. Abstinence reduces engagement of brain regions essential for cognitive control and individuals with lower levels of response inhibition are less able to resist palatable foods, and are more vulnerable to overeating. Working memory is important to keep goals in mind and for efficient use of behavior change tools, yet it can be depleted by efforts to manage cravings. This will be the first study to integrate these concepts and to explore brain mechanisms underlying a behavioral activation intervention (BAS+) to promote smoking cessation and mitigate PCWG.

This neuroimaging study will aim to examine a sub-set of the randomized clinical trial participants. Functional magnetic resonance imaging (fMRI) can identify mechanisms underlying behavior change beyond self-report and behavioral measures. We will examine neural responses in three parallel pathways including: cognitive control, food cue reactivity, and food reinforcement. As in the parent study, the primary outcomes will be food intake and 7-day point prevalence abstinence at 12 weeks post target quit date. BOLD signal (secondary outcome) will be measured at pre-treatment (week -2) and end of treatment (week 8). Our three aims address: 1) identifying putative brain mechanisms underlying BAS+ (vs. SC) treatment for smoking cessation and PCWG; 2) evaluating the relative contribution of treatment-induced changes in task related brain signal (Food Cue Response, Food Reinforcement/Choice) in prediction of post treatment food intake; and 3) testing whether BAS+ (vs. SC) induced change in neural responses to food cues and food reinforcement is a stronger predictor of food intake among smokers with greater cognitive control. The findings will address *why* BAS+ may be effective in managing PCWG and provide insight into which patients are best supported by this treatment. We also test whether cognitive control processes moderate the influence of BAS+ treatment on food intake.

1.3 *Background- Microbiome Sub-Study*

The Gut Microbiome May Underpin the Substitution of Food for Cigarettes After Smoking Cessation: Converging research suggests that the gut microbiome may play an important role in modulating post-cessation increases in food intake and set the stage for smoking relapse. Gut bacteria and the brain have a bi-directional route of communication through the microbiome-gut-brain (MGB) axis. As such, smoking cessation-induced perturbations in the gut microbiome have the potential to impact the brain as well as behavior. Preliminary research has shown that smoking cessation results in profound changes in gut microbial abundance within 4

CONFIDENTIAL

This material is the property of the University of Pennsylvania. Do not disclose or use except as authorized in writing by the study sponsor

to 8 weeks after quitting smoking (see Aim 1). These smoking cessation-associated changes (e.g., reduced *Bacteroides*, increased *Firmicutes*) are similar to those observed in obesity.

Smoking cessation-induced changes in the abundance of gut bacteria likely have functional, downstream consequences for dietary intake and smoking abstinence. Gut microbes secrete neurotransmitters and other neuroactive metabolites that regulate reward-seeking behavior by communicating pleasure and satiety to the brain via the vagus nerve. For example, dopamine, serotonin, and gamma-aminobutyric acid (GABA), as well as their precursors (tyrosine, tryptophan, and glutamate, respectively), are secreted by multiple genus. Indeed, the gut is a significant source of these key neurotransmitters that are also active in the brain. The gut microbiome also produces neuroactive metabolites (e.g., indole and short chain fatty acid propionate) that impact appetite by stimulating the production of gut hormones with anorectic functions. Shifts in the abundance of bacteria that produce these neurotransmitters and metabolites likely translate to a reduction in these molecules that are involved in reward and appetite regulation. In turn, reduced reward and appetite regulation may drive the substitution of cigarettes with palatable snack foods, as well as smoking relapse.

Can BAS+ Mitigate the Effects of Gut Microbiome Changes on Dietary Intake and Smoking Relapse? Smoking cessation induced changes in the composition of the gut microbiome along with downstream reductions in neuroactive metabolites involved in reward regulation and appetite control likely result in increased food intake (and ultimately weight gain) and smoking relapse. As such, the gut microbiome may provide a biological basis for the observation that smoking cessation heightens the reinforcing value of snack foods, which predicts subsequent food intake and weight gain. In the context of fewer alternative reinforcers and diminished sensitivity to these reinforcers, there is little to compete with food or cigarettes as a reinforcer. BAS+ focuses on increasing the number of, and pleasure derived from, alternative reinforcers to improve cessation rates, mitigate increases in dietary intake, and lesson PCWG. We will explore whether BAS+ (versus SC) mitigates the effects of gut microbiome changes on dietary intake and smoking abstinence at 12 weeks post TQD.

2 Study Objectives

2.1 Parent (Main) Study

Aim 1: To evaluate the efficacy of BAS+ versus SC when delivered in conjunction with TN.

H1a: Compared to SC, participants in the BAS+ group will have less post-cessation food intake and gain less weight at week 26.

H1b: Compared to SC, participants in the BAS+ group will have higher smoking cessation rates at the end of treatment and at the 12- and 26-week follow-up time points.

Aim 2: To examine the mechanisms by which BAS+ reduces PCWG and promotes smoking cessation.

H2a: BAS+ vs. SC will increase engagement in and enjoyment from alternative reinforcers, and reduce the relative reinforcing value of food, food reward, and food cue-induced craving after smoking cessation.

H2b: Changes in these measures will predict reduced food intake and weight gain, which in turn will predict increased quit rates.

Exploratory Aim: We will explore whether women, or smokers with greater pre-treatment weight concerns or depression symptoms are more likely to exhibit PCWG and more likely to benefit from BAS+ vs. SC.

CONFIDENTIAL

This material is the property of the University of Pennsylvania. Do not disclose or use except as authorized in writing by the study sponsor

The proposed study breaks new conceptual and empirical ground by: (1) providing the first evaluation of the efficacy of BAS+ for smoking cessation and PCWG as an adjunct to the most widely used pharmacotherapy for smoking cessation and (2) examining the mechanisms by which BAS+ reduces food intake and weight gain. If the hypotheses are supported, the findings would suggest that targeting reward-related mechanisms common to both smoking and eating: (1) is an effective approach to promoting smoking cessation, while minimizing PCWG; and (2) is a viable approach for addressing two rewarding behaviors concurrently, without risking compensatory increases in one of those behaviors. Pretreatment assessments will enable the identification of potential individual differences in intervention efficacy.

2.2 Neuroimaging Sub-Study

Aim 1: Identify putative brain mechanisms underlying BAS+ (vs. SC) treatment for smoking cessation and PCWG.

H1a: BAS+ (vs. SC) will decrease food cue-induced activity in insula, anterior cingulate cortex (ACC), orbitofrontal cortex (OFC), and ventral striatum/accumbens (VS/NAC);

H1b and H1c: (Hb) BAS+ (vs. SC) will decrease food reinforcement choice-related activity in VS/NAC and ventromedial prefrontal cortex (vmPFC); and **(H1c)** will produce corresponding decreases in food craving, reward, and reinforcement at the behavioral level (task performance).

Aim 2: To evaluate the relative contribution of treatment-induced changes in task related brain signal (Food Cue Response, Food Reinforcement/Choice) in prediction of post treatment food intake.

H2a: Brain network response (H1a-b) in the BAS+ (vs. SC) group will characterize treatment-induced changes in caloric intake (and quit success) more accurately than clinical (age, sex, nicotine dependence, BMI) and behavioral (withdrawal, craving, food reinforcement) measures alone.

H2b: The relative contribution of domain specific brain signal (food cue reactivity and food reward) to the prediction of treatment-induced change in caloric intake will be evaluated (regression model).

Aim 3: Test whether BAS+ (vs. SC) induced change in neural responses to food cues and food reinforcement is a stronger predictor of food intake among smokers with greater cognitive control.

We predict that the relationship of food cue and choice-related neural activity (e.g., VS/NAC BOLD signal; BAS+ vs. SC) will be a stronger predictor of caloric intake among smokers who also show greater working memory-related neural activity (i.e., DLPFC BOLD signal) at baseline and post treatment. Regions of interest for food cue and choice-related neural activity will be selected from those shown to be sensitive to cessation in Aim 1.

Utilizing fMRI, we can identify the neural underpinning of a novel behavioral activation (BAS+) intervention for smoking and related PCWG. The findings will address *why* BAS+ may be effective in managing PCWG and provide insight into which patients are best supported by this treatment. We also test whether cognitive control processes moderate the influence of BAS+ treatment on food intake. If our cognitive control hypothesis is supported, combining neurocognitive training with BAS+ could improve treatment efficacy. The integration of concepts and tools from behavioral economics and cognitive neuroscience tackles PCWG in a highly novel way, with implications for validating new treatments.

CONFIDENTIAL

This material is the property of the University of Pennsylvania. Do not disclose or use except as authorized in writing by the study sponsor

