6.8 Sample Size Determination - Neuroimaging Sub-Study

We plan to test hypotheses at a global 5% Type I error (alpha) for each family of hypotheses, and have chosen a completed sample ($N=60$) that will achieve at least 80% power using 2-sided tests. Our analysis of power was based on “effect size” (standardized difference). Effect sizes were calculated from our own preliminary data, from published data summaries, and from published estimates of effects (e.g., t statistics, coefficients, p-values) using validated summary methods. We have several hypotheses and more than one outcome measure for some (e.g., different brain regions). We will control error in a family-wise manner, adjusting alpha (Bonferroni Aims 1 and 2, Hochberg step-up procedure for Aim 3) for the number of tests within each hypothesis family. Bonferroni corrections will also be adjusted for the correlations among multiple outcomes.

Aim 1 includes 2 hypotheses (**H1a&b**) regarding treatment effects on neural responses including 5 ROIs responding to food-related tasks. We test at $p<0.02$ because of the high correlation among ROIs within subjects ($\rho=0.54$). Estimates of effect size from our center data ($d=0.36$) indicate that we have 80% power to detect the effects. Aim 1 also tests hypothesis **H1c** for cessation effects. At the Bonferroni corrected threshold of $p=0.0167$, we have 80% power to detect small to medium effect sizes ($d=0.37$).

Aim 2 (H2a&b) essentially tests for mediation. The hypothesis that cessation increases food intake will be tested at 0.05, with power for effect sizes $\sim d=0.32$ [9, 58]. For Aim 2b (ROIs predicting food intake), we expect a weaker correlation than H1a ($\rho=0.4$), and our adjusted threshold for significance is $p<0.01$. Expected effect sizes are approximately 0.5, and we expect 96% power to detect the effects.

Aim 3 begins with the model in Aim 2b above, and tests interacting effects of working memory-related BOLD signal and food reinforcement (or food cue reactivity) on food intake. We will reduce the complexity of this analysis by using difference scores (pre minus post) to model a 2-

CONFIDENTIAL

This material is the property of the University of Pennsylvania. Do not disclose or use except as authorized in writing by the study sponsor

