Aim 1: Identify effects of BAS+ (vs SC) treatment on food related neural activity and behavior: These comparisons are all between subject, and will be analyzed using mixed models regression (xtmixed, StataCorp, Texas). The model predictors will include a binary indicator for group (BAS+ vs. SC). The hypothesis will be tested using the z-score corresponding to the main effect of group. Covariates can be included in the model to control error (sex, BMI, nicotine dependence, age, weight concerns), although we do not expect to make large gains for adding subject-level controlling variables in a mixed model.

Aim 2: Evaluate the relative contribution of these neural processes to post-cessation caloric intake: Our outcome variable is average daily calories based on food recalls. The first comparison (pre vs. post-treatment) is within-subject, and will be analyzed using mixed models regression with subject specific random effects. As before, we include a binary predictor for condition, a categorical indicator for serial day, and we will test using the z-score corresponding to condition. For testing candidate mediators, we will again model calories using mixed models, entering variables as time-varying (condition varying) predictors, along with subject specific random effects. Finally, we will build the larger model, looking for confounding that represents potential mediation. For this purpose, we will use regression-based multi-equation path models. Path Analysis partitions a directly measured bivariate relationship, for example, between abstinence and calories ingested, into direct and indirect causal paths, to tease apart the important components mediating the response. We will deem that mediation has occurred when a relationship between abstinence and food intake accounted in full, or in part, by one or more of the intervening variables (BOLD signal change or subjective responses in cessation vs. smoking). We will assess the strength of the indirect effects through confidence intervals, evaluate the proportion mediated (i.e., partial or complete mediation), and determine significance with Delta method standard errors. To assess the level of mediation for a pathway, we will estimate the ratio of the indirect effect to the total effect (i.e., effect proportion mediated $\beta_{\text{indirect}}/\beta_{\text{total}}$).

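### Neuroimaging H2a claims better accuracy than clinical and behavioural measures, but no planned analysis compares accuracy or models quit success

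*Combined protocol and SAP*

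**What the plan says.** Section 2.2, Aim 2, H2a, comparing BAS+ with SC, predicts of brain network response that it "will characterize treatment-induced changes in caloric intake (and quit success) more accurately than clinical (age, sex, nicotine dependence, BMI) and behavioral" measures. The behavioural measures are listed as "withdrawal, craving, food reinforcement) measures alone". The hypothesis thus names four clinical and three behavioural comparators and two outcomes, caloric intake and quit success.

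H2b, in the same section, concerns how much the food-cue and food-reward signals each contribute "to the prediction of treatment-induced change in caloric intake will be evaluated (regression model"). It sets brain domains against each other, not brain against clinical or behavioural measures.

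Section 6.8 says that Aim 2, covering H2a and H2b, "essentially tests for mediation". It then gives power for two things. "The hypothesis that cessation increases food intake will be tested at 0.05", with an effect size of about 0.32. Regional signals predicting intake (Aim 2b) are tested at 0.01, with an expected effect of about 0.5 and 96% power.

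Section 6.11, Aim 2, names average daily calories as the outcome. It describes a pre/post mixed model, then mixed models with candidate mediators as time-varying predictors, then a path model: "Finally, we will build the larger model, looking for confounding that represents potential mediation". Inference rests on indirect effects, the proportion mediated and Delta-method standard errors. The listed clinical measures appear only under Aim 1, as optional covariates.

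**The concern.** H2a is a comparison. To test it, the plan needs a reference model without the brain measures, a model with them, a measure of accuracy, and a rule for deciding. Sections 6.8 and 6.11 supply none of these, and the quit-success half of H2a has no Aim 2 model at all.

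A mediation analysis answers a different question. A significant indirect effect, or a large mediated proportion, says that part of an association with intake runs through the brain signal. It does not say that the signal predicts intake better than age, sex, dependence, BMI, withdrawal, craving and food reinforcement do. The same gap would remain if a treatment-arm term were added to the Aim 2 models.

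At stake is whether the sub-study can report on H2a. Either the hypothesis goes unanswered, or a criterion is chosen after the data are seen. With about 50 to 60 people and a dozen predictors, that choice can settle the answer.

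**Working it through.** **Hypothesis against analysis**

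| H2a needs | Sections 6.8 and 6.11 provide |
|---|---|
| Reference model with the seven named measures | None; the clinical measures are optional Aim 1 covariates |
| Accuracy measure | None; indirect effects and proportion mediated |
| Comparison or validation | None |
| Model for caloric intake | Yes |
| Model for quit success | None |

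**The plan's own figure.** There is no power figure for H2a's comparison. The only fully specified Aim 2 figure is the 96% for Aim 2b. Read as a one-sample test at N = 60, d = 0.5, two-sided 0.01, power is Φ(0.5 × √60 − 2.576) = Φ(1.297) = 90%. Read as a correlation of 0.5, it is 94%. Neither reproduces 96%, but that figure concerns a different test and nothing below depends on it.

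**Inputs.** Comparators: 4 + 3 = 7 (section 2.2). Brain predictors: 5, since section 6.8 refers to Aim 1 hypotheses "including 5 ROIs responding to food-related tasks"; 6 if the ventral striatum is counted once for each task. N: about 50 (section 3.2) or 60 (section 6.8). Correlation among regions: 0.54 (section 6.8). Assumption, not in the documents: R-squared of the seven measures is 0 or 0.20.

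**Why an unstated criterion matters.** When no predictor has any effect, adding k useless predictors raises in-sample R-squared on average by k/(N − 1).

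- k = 5: 5/49 = 0.102 at N = 50; 5/59 = 0.085 at N = 60.
- k = 6: 6/49 = 0.122; 6/59 = 0.102.

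Simulation (4,000 datasets per setting, one row per person, ordinary least squares) gave the same averages. With R-squared of 0.20 for the seven measures, the gain from five useless regions was about 0.08 and 0.07.

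How often useless brain measures come out ahead, by criterion:

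| Criterion | Brain favoured |
|---|---|
| Raw R-squared, brain added to the seven | 100% |
| Adjusted R-squared, brain added | 42–45% |
| Leave-one-out error, brain added | 7–9% |
| Nested F-test at 0.05, brain added | 4–6% |
| Raw R-squared, brain alone vs the seven, no effects | 31–42% |
| The same, seven measures at R-squared 0.20 | 2–6% |

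**If the brain measures do help.** With a true added R-squared of 0.10 and 0.20 for the seven measures (both assumed), lower leave-one-out error favours the larger model in 45–54% of datasets across N = 50 to 60, and the F-test rejects in 38–48%. In a further run with these settings (five regions correlated 0.54, 1,000 datasets, 199 permutations of the regional block), a permutation p-value of 0.05 or less on leave-one-out error was reached in 36% at N = 50 and 46% at N = 60, and in about 4% when the regions were useless. The recommended rule therefore has about the power of the F-test.

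**Quit success.** Sub-study quit rates at 12 weeks are not given. As an illustration, section 6.7's 26-week rates of 13% and 25% with equal arms average 19%, or 9.5 quitters in 50 and 11.4 in 60. That is too few for an unpenalised logistic model with 7 to 12 predictors.

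**The case against.** A reader might infer that the plan will declare H2a supported because a model with more predictors fits better. The documents do not say so. Section 6.11 uses z-scores, confidence intervals for indirect effects and Delta-method standard errors, none of which rewards a predictor merely for being present. The larger model it mentions is the path model, not the bigger of two models compared on fit.

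A reader might also infer that in-sample fit always favours the brain measures. That is true only of unpenalised fit when they are added to the seven. It fails for adjusted R-squared, for an F-test, and for brain measures used in place of the seven. H2a's wording suggests the added reading but does not settle it.

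Nor is it right that only mediation models are planned. Section 6.11 includes mixed-model regressions, and its intervening variables include subjective responses as well as BOLD signal.

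These objections limit the claim; they do not close the gap, because none of those models compares accuracy. Two further objections carry weight. The simulation uses one row per person, whereas section 6.11 specifies repeated-measures models, so its figures are illustrative. Cross-validation also has modest power at this size, but an in-sample F-test does no better. Finally, this is one hypothesis of a sub-study and does not touch the parent trial's primary outcomes.

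**Conclusion.** The mismatch stands on the text alone. H2a asserts superior accuracy for two outcomes; the analysis assigned to it is a set of mixed and mediation models for one outcome, and these cannot confirm or refute the assertion.

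The spurious R-squared gain of about 0.10 (N = 50) or 0.085 (N = 60) is conditional. It applies if raw R-squared of nested models were used, with five regions and no true effects. It shows why the criterion must be fixed in advance; it does not describe a bias in the plan as written. The power range of about 38 to 54% rests on an assumed true gain of 0.10 and an assumed R-squared of 0.20 for the seven measures, and the recommended rule sits in the lower part of that range or just below it. The sponsor should correct this before the Aim 2 analysis; the parent trial is unaffected.

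**What to change.** In section 6.11, add an analysis for H2a:

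1. Model (a): the seven named clinical and behavioural measures. Model (b): the same plus one fixed list of regional signal changes. State the list, since section 6.8 counts five regions while section 6.11 gives two as primary for the food tasks.
2. Fit both for change in kcal/day (linear) and for abstinence (logistic) at a named time point; section 1.2 points to 12 weeks. With few quitters, use penalisation or a reduced regional summary.
3. Use one decision rule per outcome: the reduction in cross-validated error from (a) to (b), with a permutation p-value from permuting the regional block across participants. Use squared error for kcal/day, and Brier score or log-loss for abstinence. Give the threshold.
4. Keep the mediation models as a separate analysis.

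The simpler alternative is to restate H2a as a mediation hypothesis and drop the claim of greater accuracy.

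Cost: a short addition to the plan and some code, with no new data. Reported performance will look less favourable than in-sample fit, and a modest real contribution from the brain measures may well be missed at this sample size; the plan should say so.
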